16.5 Reporting Serious Adverse Events and Product Technical Compliances

Any Serious Adverse Event or PTC, including death, that occurs during this study, whether or not the event is considered to be related to the study product or surgical procedure, must be reported within 24 hours after the site becomes aware of the event to the Safety Monitor (ProPharma Group/PROSAR or designee).

The contact information for reporting SAEs is as follows for the US and Ukraine:

ProPharma/Group PROSAR Email: [contact] [contact]

The contact information for reporting SAEs is as follows for Japan:

[contact]

The Investigator is encouraged to discuss with the Unblinded Medical Monitor any adverse experiences for which the issue of reportability is unclear or questioned.

A verbal SAE notification must be followed by a completed Serious Adverse Event Report form signed by the Investigator within 24 hours. The report should be as complete as possible without delaying ProPharma Group/PROSAR notification.

Any SAE follow-up information requested by ProPharma Group/PROSAR or designate should be provided in a timely manner.

Upon receipt of notification of any Serious Adverse Event, ProPharma Group/PROSAR, the Unblinded Medical Monitor and the Sponsor will immediately conduct an evaluation of the event and take action indicated by the results of the evaluation. This may include notification of applicable regulatory authorities/federal agencies, other Investigators, IRBs, IBCs and/or the suspension or termination of the study. The Sponsor will remain blinded during this process.

The Investigator is required to report all IND Safety Reports to the local Ethics Committee (EC) or Institutional Review Board (IRB) and Institutional Biosafety Committee (IBC) in accordance with the EC/IRB/IBC by laws.

All additional follow-up evaluations of the SAE must be reported to ProPharma Group/PROSAR or designee as soon as they are available.

16.6 Follow-up of Adverse Events

All AEs (both serious and non-serious) should be followed until resolution or until a stable clinical endpoint is reached. All measures required for AE management and the ultimate outcome of the AE must be recorded in the source document.

17.0 EXTERNAL DATA SAFETY MONITORING BOARD

An External Data Safety Monitoring Board (DSMB) will evaluate efficacy and toxicity and mortality rates, and recommend appropriate actions, according to the DSMB Charter. The DSMB will review ongoing study data within one month of the enrollment of subjects at the 25%, 50%, 75% and 100% of the total population.

18.0 STATISTICAL METHODS

18.1 Analysis Populations

18.1.1 Modified Intent-to-Treat Population

The Intent-to-Treat (ITT) population will include all randomized patients. All efficacy analyses will be conducted on modified ITT (mITT) population, which is defined as all randomized patients who complete the surgical procedure. In analyses based on the mITT population, subjects will be analyzed according to their randomized treatment assignment. Analyses based on the mITT population will be considered the primary analyses of efficacy.

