9.4 Cell Administration or Sham Surgery (Visit 3: Day 1)

Subjects can be admitted to the clinical site on Day -1 and undergo study surgical procedure on Day 1. Prior to any procedures, the patient will be queried on the use of any or changes in medication or adverse events that have occurred since Baseline.

The patient will be randomized prior to surgery via IWRS. The surgical staff, especially the surgeon, should make every effort to remain blinded to the assigned treatment until the start of the surgical procedures. The patient's group allocation will be known by the unblinded laboratory staff so that the appropriate SB623 dose can be prepared for the patient (if randomized to Group 1).

Prior to cell implantation, either a head CT overlaid with the Baseline head MRI or a head MRI alone will be done to determine the exact locations for the implants. Both International Normalized Ratio of Prothrombin Time (INR) and Activated Partial Thromboplastin Time (APTT) shall be performed in the local lab prior to surgery, both results must be normal according to local lab (e.g. INR >1.2 and APTT >38 seconds).

Group 1:

One burr hole will be made in the skull of the patient in a location that will allow ready access adjacent to the focal area of injured brain tissue region. Cells will be implanted using 3 needle tracks with 5 cell deposits for each track at varying depths. Cell implantation will be standardized as to volume (20 μ L/deposit) and rate (10 μ L /min), with spacing between each implant of approximately 5-6 mm.

Group 2:

Subjects will be given procedures similar to Group 1, except will be given a sham surgery (light sedation, stereotactic procedure, partial-thickness skull outer table burr hole, scalp suture, but no penetration of inner table or dura mater).

After cell implantation or sham surgery, the following will be performed:

- Imaging (head CT only)
- Adverse Events
- Concomitant medications

Protocol TBI-01 Version 5, May 17, 2018

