10.4 Preparation and Administration

Details for preparation of the cell suspension for administration and for loading the syringe in the Operating Room (OR) will be provided by the Sponsor. Clinical sites will be provided necessary materials for reconstitution of the cells and will be trained by the Sponsor. The cryopreserved cells will be thawed, washed, centrifuged, and re-suspended in Plasma-Lyte A at varying concentrations for administration to the patient within approximately 3 hours of dose release. Prior to administration, a gram stain and a test for endotoxin will be done and a sterility test initiated on the last cell wash to ensure continued sterility. If the endotoxin level is > 5 EU/mL or the gram stain is positive, implantation will not occur. If the sterility test is positive, an investigation will be conducted to determine the source of the contamination by the sponsor. In addition, identification of the patient will be followed closely for adverse events associated with a possible infection and response to antimicrobial therapy, including frequent clinic visits until any infection is cleared.

This Investigational Product may not be used for any purpose other than this clinical study.

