18.1.3 Safety Population

The safety population will include all study patients who undergo surgery (implant or sham). All safety analyses will utilize this population. In analyses based on the safety population, subjects will be analyzed according to the actual treatment received.

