6.0 ANALYSIS POPULATIONS

6.1 Modified Intent-to-Treat Population

The Intent-to-Treat (ITT) population will include all randomized patients. All efficacy analyses will be conducted on the modified ITT (mITT) population, which is defined as all randomized patients who complete the surgical procedure. In analyses based on the mITT population, subjects will be analyzed according to their randomized treatment assignment. Analyses based on the mITT population will be considered the primary analyses of efficacy.

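### The primary efficacy set drops randomised patients who do not complete surgery, at least one cause of which can arise only in the SB623 arm, and no efficacy analysis of all randomised patients is planned

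*Protocol*

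**What the plan says.** **Order of events.** Protocol 9.4 (Visit 3, Day 1): "The patient will be randomized prior to surgery via IWRS". The same section says that the laboratory staff know the allocation so that they can prepare a dose for a Group 1 patient.

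**Release rule.** Protocol 10.4, repeated in the synopsis: "If the endotoxin level is > 5 EU/mL or the gram stain is positive, implantation will not occur".

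**Populations.** Protocol 18.1.1 begins "The Intent-to-Treat (ITT) population will include all randomized patients" and continues "All efficacy analyses will be conducted on modified ITT (mITT) population", "which is defined as all randomized patients who complete the surgical procedure". SAP Appendix A, section 6.1, agrees: "All efficacy analyses will be conducted on the modified ITT (mITT) population". Both call mITT primary and analyse it by randomised arm. Neither defines what counts as completing the procedure.

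**Other sets.** Per Protocol (Protocol 18.1.2) is randomised patients without major violations. As Treated (SAP Appendix A, section 6.4) is randomised patients who undergo surgery, analysed by treatment received, and is used only if an ITT patient gets no treatment or the wrong one. In the SAP's list of outputs, ITT serves disposition and listings.

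**Replacement.** Protocol 18.6 and SAP Appendix A, section 3.4, continue enrolment until about 52 patients are in mITT.

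**The concern.** Randomisation balances the arms only at the moment of allocation. A rule that removes patients afterwards is harmless if it works alike in both arms. It is not safe when one arm has causes of removal that the other lacks.

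That is the case here. Sham surgery involves no cell product and does not breach the inner table or dura (Protocol 6.0), so a sham patient cannot lose an implant to a failed release test. Nor can a sham patient have an intradural complication during implantation. Replacement then fills the gap with patients who did complete surgery, so the final mITT count does not show the loss.

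At stake is whether the primary estimate compares the groups as randomised. If patients harmed during implantation were among those removed, the SB623 mean would be too favourable, and no planned model would reveal it.

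**Working it through.** **1. The plan's own sample size.** Inputs from Protocol 18.6: mean changes 10.0 and 3.0, SD 7.25, two-sided alpha 0.05, power 80%, ratio 3:1.

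- Control n = (4/3) × [7.25 × (1.96 + 0.842)/7]² = 11.23, rounded up to 12. SB623 n = 36. Total 48, as stated.
- Noncentral-t power at 36:12 is 80.9%.
- 48 × 1.08 = 51.84, or about 52, as stated. At 3:1 that is 39:13, with power 84.0%.

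The planned figures reproduce. The point is about who is analysed, not about the sample size.

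**2. Does any planned efficacy analysis cover all randomised patients by randomised arm?**

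| Set | Product fails release, never operated on | Implant started, then aborted | Arm used |
|---|---|---|---|
| mITT | out | out, if aborting counts as not completing | randomised |
| As Treated | out | probably in | treatment received |
| Per Protocol | depends on the violation review | depends on the violation review | randomised |
| ITT | in | in | no efficacy model planned |

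The addendum's sensitivity analysis of the primary endpoint removes one patient with an imputed baseline and stays within mITT. Section 6.4 remarks that As Treated results would otherwise match those for ITT, but no ITT efficacy model is specified.

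**3. Illustration of size.** The documents give no rate of release failure or aborted implantation, so the number excluded, m, and their mean change, c, are assumptions. Take 39 SB623 completers at 10.0, 13 sham patients at 3.0, and restore m SB623 non-completers:

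ITT difference = (39 × 10 + m × c)/(39 + m) − 3

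- m = 2, c = 3 (like sham): 396/41 − 3 = 6.66
- m = 4, c = 3: 402/43 − 3 = 6.35
- m = 2, c = 0 (no change): 390/41 − 3 = 6.51
- m = 4, c = 0: 390/43 − 3 = 6.07

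For power, let N = 39 + m and p = m/N. The SB623 variance becomes 7.25² + p(1 − p)(10 − c)², which is pooled with 7.25² for sham and used in a noncentral t with N + 11 degrees of freedom.

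| m | c | Difference | Power |
|---|---|---|---|
| 0 | – | 7.00 | 84.0% |
| 2 | 3 | 6.66 | 79.6% |
| 4 | 3 | 6.35 | 75.1% |
| 2 | 0 | 6.51 | 76.4% |
| 4 | 0 | 6.07 | 68.8% |

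**4. Chance that the problem arises at all.** P(at least one of 39) = 1 − (1 − q)³⁹. For assumed q of 1%, 2% and 5% this is 32.4%, 54.5% and 86.5%.

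**The case against.** Several stronger readings are tempting, and the documents do not carry them.

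- *Non-completers vanish from every efficacy analysis.* This is not established. As Treated requires only that surgery was undergone, so it may recover a patient whose implant was started and abandoned. Per Protocol is not worded to require completion. Neither replaces ITT: As Treated omits patients never operated on and groups by treatment received, and Per Protocol is a selected set.
- *The exclusion must favour SB623.* This is not shown. The one explicit SB623-only cause is a property of the cell preparation, with no stated link to prognosis. The favourable direction needs patients harmed during implantation to be classed as non-completers, and the documents contain neither an abort rule nor a definition of completion.
- *The distortion is large.* Four exclusions who each worsen by 5 points would lower the SB623 mean to (390 − 20)/43 = 8.6, which is 1.4 below plan. That joins a high assumed count to a bad assumed outcome. Protocol 2.3.3 reports surgical complications below 1% in over 2,650 stereotactic patients. At 1%, even if every complication stopped surgery, the chance of 2 or more in 41 is about 6%, and of 4 or more in 43 about 0.1%. That source does not cover release failure, for which no rate is given. When c = 3, the drop is dilution by untreated patients, not hidden harm.

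Three more points deserve weight. Sedation problems, abnormal coagulation results on Day 1 or withdrawal can stop surgery in either arm. Surgeons are asked to stay blinded until the procedure starts, which limits selective cancellation. ITT disposition and listings already show part of what happened.

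These objections limit the claim about direction and size. They do not supply a comparison of all randomised patients by randomised arm.

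**Conclusion.** The point holds in a limited form. The primary set conditions on a post-randomisation event, at least one documented cause of which is confined to SB623, and no planned efficacy analysis restores the full randomised comparison. Protocol 11.0 speaks of a suspension for each subject, which sits awkwardly with 9.4, but a failed test still stops only an implantation, and sham has none.

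The exclusion can bias the estimate, and would favour SB623 if those excluded were harmed during implantation. Its size is unknown, and it is zero if every randomised patient completes surgery. Under the assumed 2 to 4 exclusions who change like sham or not at all, the planned difference falls by 0.34 to 0.93 points. That would not overturn a 7-point effect, but it can take power below 80%. With 13 sham patients a few exclusions matter, and a sensitivity analysis is warranted.

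**What to change.** 1. **Add an ITT MMRM of the primary endpoint**, by randomised arm, as a sensitivity analysis using the primary model. This is the essential step.
2. **Collect Week 24 FMMS from every randomised patient**, whether or not surgery was completed. Without post-baseline data, a patient adds nothing to the change-from-baseline MMRM.
3. **Base mITT on surgery started rather than completed**, and define that point. This keeps aborted implants in the primary set. It does not replace step 1, because a release failure found before surgery starts would still remove only SB623 patients.
4. **Tabulate post-randomisation exclusions from mITT by arm and reason**, extending the planned ITT disposition table.

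The cost is protocol and SAP wording, follow-up of a few non-completers, one more model run and a possibly slightly less favourable estimate. The SAP addendum already refers to unblinded interim results. If data collection has closed, steps 1 and 4 can still go into the study report, using whatever FMMS data exist for non-completers and labelled as added after that unblinding.

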18.1.2 Per Protocol Population

The Per Protocol (PP) population will include all randomized patients who have no major protocol violations. Major protocol violations will be identified based on blinded data after the study is completed, but before database lock and the unblinding of the treatment group assignments. All efficacy analyses will be repeated on this population. In analyses based on the PP population, subjects will be analyzed according to their randomized treatment assignment. Analyses based on the PP population will be considered secondary analyses of efficacy.

18.1.3 Safety Population

The safety population will include all study patients who undergo surgery (implant or sham). All safety analyses will utilize this population. In analyses based on the safety population, subjects will be analyzed according to the actual treatment received.

18.2 Statistical Analysis

The Statistical Analysis Plan (SAP) will provide details on the statistical methods planned for this study, and it will be finalized prior to the clinical study database being locked and the treatment being unblinded.

In general, continuous variables will be summarized by the following descriptive statistics: sample size, mean, median, standard deviation, minimum, and maximum. Categorical variables will be summarized by frequencies and percentages (contingency tables). The three SB623 dose groups will be pooled for all analyses, except where noted otherwise.

18.2.1 Demographic and Baseline Characteristics

Demographics and baseline characteristics will be summarized by treatment group using descriptive statistics for continuous variables and frequencies and percentages for categorical variables.

18.2.2 Analysis of Efficacy

All efficacy analyses will be performed on the mITT and PP populations. The efficacy endpoints are to be analyzed per the SAP.

18.2.2.1 Primary Efficacy Endpoint Analysis

The primary analysis will be a comparison of the mean change from baseline in the Fugl-Meyer Motor Scale score of SB623 treated subjects (pooling all SB623 doses) to sham surgical controls at 24 weeks. A mixed model repeated measures (MMRM) analysis will be performed with terms for treatment, visit, the baseline Fugl-Meyer Motor Scale score, the GOS-E score at screening, and the treatment-by-visit interaction. The Restricted Maximum Likelihood Estimation procedure will be employed using an unstructured covariance matrix. Missing observations will not be imputed.

Protocol TBI-01 Version 5, May 17, 2018

18.2.2.2 Secondary Efficacy Endpoint Analyses

Secondary analyses will evaluate a number of outcomes:

- A. Comparison of the mean change from baseline in the Disability Rating Scale (DRS) score of SB623 treated subjects (pooling all SB623 doses) to sham surgical controls at 24 weeks will be performed in a manner analogous to that for the primary efficacy endpoint.
- B. Comparison of the mean change from baseline in the Action Research Arm Test (ARAT) total score of SB623 treated subjects (pooling all SB623 doses) to sham surgical controls at 24 weeks will be performed in a manner analogous to that for the primary efficacy endpoint. This analysis will be based on upper extremity deficit patients only.
- C. Comparison of the mean change from baseline in Gait Velocity of SB623 treated subjects (pooling all SB623 doses) to sham surgical controls at 24 weeks will be performed in a manner analogous to that for the primary efficacy endpoint. This analysis will be based on lower extremity deficit patients only.
- D. Comparison of the mean change from baseline in the two NeuroQOL subdomain T scores of SB623 treated subjects (pooling all SB623 doses) to sham surgical controls at 24 weeks will be performed in a manner analogous to that for the primary efficacy endpoint. The two subdomains include:
 - a. Upper Extremity Function (Fine Motor ADL)
 - b. Lower Extremity Function (Mobility)

The analysis of the Upper Extremity Function domain will be based on upper extremity deficit patients only, and the analysis of the Lower Extremity Function domain will be based on lower extremity deficit patients only.

E. The proportion of SB623 treated subjects (pooling all SB623 doses) scoring either 7 (much better) or 6 (a little better, meaningful) on the Global Rating of Perceived Change by both Subject and Clinician will be compared to sham-surgery controls at 24 weeks (from Baseline) using a logistic regression model with treatment (SB623 vs. sham placebo), the baseline Fugl-Meyer Motor Scale score, and the GOS-E score at screening as terms in the model. The outcome variable of this analysis is a dichotomized variable based on of the Global Rating of Perceived Change score (≥6 vs. <6).

In addition, each efficacy endpoint mentioned above will be analyzed to examine dose response. Similar statistical methodologies to those used to evaluate SB623 combined doses versus the surgical sham control will be used for each efficacy endpoint, except that dose will be included as a term in the model instead of treatment. Dose will be a continuous variable with the control treatment assigned a value of 0.

18.2.2.3 Exploratory Efficacy Analyses

The analyses of exploratory efficacy endpoints will be detailed in the SAP.

18.2.2.4 Subgroup Analysis

Inferential analyses will be performed on some subgroups of interest. Details of the subgroup analyses will be included in the SAP.

18.3 Analysis of Safety

All safety analyses will be performed on the safety population.

Adverse events (AEs) will be summarized by presenting, for each treatment group, the number and percentage of patients having any adverse events, having an adverse event that led to

Confidential and Proprietary

discontinuation from the study, having an adverse event in each System Organ Class (SOC) and having each individual type of adverse event (Preferred Term). These analyses will also be performed for serious adverse events (SAEs). Adverse events will also be summarized at the event level by severity, by relationship to study product or surgery, and by action taken. Other information collected will be listed. The summary of AEs will be limited to treatment emergent AEs (TEAEs), which are defined as any adverse event with onset on or after the initiation of treatment or any adverse event already present that worsens in intensity following exposure to study treatment.

For each treatment group, descriptive statistics will be presented by visit for the actual values and the changes from baseline for each quantitative laboratory test. The difference between treatment groups in the mean change from baseline will also be presented. For each laboratory test and each treatment group, the one- sample t-test will be used to test whether the mean change from baseline equals 0 for each post-baseline time point. The two-sample t-test will be used to test whether the mean changes from baseline are equal for the two treatments. A shift table will summarize changes in status (normal, abnormal) from baseline to each post-baseline time point for each laboratory test, and abnormal lab values will be flagged in the data listings.

For each treatment group, descriptive statistics will be presented by visit for the actual values and the changes from baseline for each vital sign. The difference between treatment groups in the mean change from baseline will also be presented. For each vital sign and each treatment group, the one-sample t-test will be used to test whether the mean change from baseline equals 0 for each post-baseline time point. The two-sample t-test will be used to test whether the mean changes from baseline are equal for the two treatments. A shift table will summarize changes in status (normal, abnormal) from baseline to each post-baseline time point for each vital sign, and abnormal values will be flagged in the data listings.

18.4 Multiplicity Considerations

Multiplicity considerations will not be taken into consideration in the analyses for this Phase 2 study.

18.5 Missing Data

Every effort will be made to reduce the number of dropouts and to document reasons for dropping out. Missing data will be discussed in the Statistical Analysis Plan (SAP).

